This is a single-center, placebo-controlled, double-blinded, parallel-group, randomized 90 days (+/- 5 days) trial to study the effect of IC-CBAS 500 mg and 1000 mg BID on EEC function, satiety perception, body weight and satiety GI hormones, in patients with APS-OB phenotype. A lifestyle intervention will be provided. These consist of an obesity physician consult, a low-calorie diet instructed by a member of the study team, and physical activity and behavioral suggestions. These interventions should last at least the length of the study. In addition, this study will include 2 colonoscopies at the beginning (i.e., before medication/placebo start) and at the end of the study (i.e., after last dose of medication/placebo) in the first 6 patients in each group willing to consent to the colonoscopies (12 patients; 24 colonoscopies in total). Participants will receive a bowel prep (Movi-prep) and follow standard colonoscopy preparation guides. The next day, after an overnight fasting, a colonoscopy with terminal ileum intubation will be performed. The colonoscopy will be done in the GI clinical or research unit and will be supported by sedation based on patients' characteristics (i.e., conscious sedation vs. anesthesia supported sedation). During the procedure, 8 biopsies will be obtained from the ilium, right and left colon. We will include otherwise healthy patients with a BMI > 30 kg/m², age range 18-65 years, and APS-OB phenotype. Based on the results of our previous trial comparing weight loss in exenatide therapy vs placebo [2], we calculated a sample size of 18 participants per group (total of 36) with 80% power, 0.05 alpha to detect a 1 kg difference between treatment and placebo groups.

Study Intervention:

Ileocolonic-release conjugated bile acid 500mg tablets will be provided by Bilarm Health Inc., San Diego, CA.

Anticipated Results:

In comparison with placebo, IC-CBAS will result in improved EEC function, increased postprandial incretin secretion, and weight loss when compared to placebo.

Significance:

We expect to demonstrate that delayed IC-CBAS increases satiety, restoring satiety in patients with APS-OB phenotype. This study will provide the basis for future pharmacological studies, exploring the effect of luminal enteroendocrine secretagogues in patients with obesity and APS-OB phenotype.

BACKGROUND:

Overview:

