We propose a single center, placebo-controlled, randomized double blinded 90 (+/- 5) day trial, to study the effect of IC-CBAS delivery (500 mg BID for the first week and 1000 mg BID for the rest of the study) on colonic EEC function, postprandial incretins (GLP-1, PYY₃₋₃₆, FGF-19, and OXM), body weight, and satiety (evaluated with gastric emptying and appetite based VAS) in patients with obesity and abnormal satiety. We plan to randomize 18 participants per group. Participants will complete the following visits: 1) Screening and Consent (virtual); 2) Baseline phenotype, lifestyle intervention, 3) Colonoscopy and Randomization visit prior to medication start (in first 6 patients in each arm) who are willing to consent to colonoscopy), 4) Two (in person or virtual) Study Team visits at 30 & 60 days post randomization, 5) Colonoscopy visit and 6) Exit Phenotype visit after taking last medication dose (in first 6 patients in each arm). During the phenotype visits, participants will be phenotyped by measuring energy expenditure, satiety with gastric emptying of solids and VAS scores, satiation with calories consumed to fullness, and emotional eating by questionnaires[8]. Resting energy expenditure will be measured by indirect calorimetry, gastric emptying will be assessed with scintigraphy and calories to fullness will be tested in *ad libitum* meal. In addition, participants will have a body composition with a DEXA scan. Blood will be collected every 30 minutes for 6 hours and selected plasma gastrointestinal hormones will be measured. A sample will be stored for venous blood DNA analysis. Stool samples will be collected for 24 hours for microbiome, bile acids and short chain fatty acids. Participants will keep a food, medication, and activity diary. Participants

will receive a bowel prep (Movi-prep) and follow standard colonoscopy preparation guides. The next day, after an overnight fasting, a colonoscopy with terminal ileum intubation will be performed. The colonoscopy will be done in the GI clinical or research unit and will be supported by sedation based on patients' characteristics (i.e., conscious sedation vs. anesthesia supported sedation). During the procedure, 8 biopsies will be obtained from the ilium, right and left colon. During the Study Team visits, patients will meet with the study team to review medication compliance, assess adverse events, and perform a medication dispensation.

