- Participants will meet with the study team (either in person at the CRTU or virtually) approximately 30 days after visit 2. The study team will assess adverse events, medication compliance, and perform a new medication dispensation (if visit is virtual the medication will be shipped to the participant's preferred address).

- **Visit 4: Study Team visit**

Participants will meet with the study team (either in person at the CRTU or virtually) approximately 30 days after visit 3. The study team will assess adverse events, medication compliance, and perform a new medication dispensation (if visit is virtual the medication will be shipped to the participant's preferred address).

- **Visit 5: Colonoscopy #2**

- Visit 5 will only be completed in the first 6 patients of each group who are willing to consent to both colonoscopy visits.
 - Participants will receive a bowel prep (Movi-prep) during visit 5 and follow standard colonoscopy preparation guides. The next day, after an overnight fasting, a colonoscopy with terminal ileum intubation will be performed. The colonoscopy will be done in the GI clinical or research unit and will be supported by sedation based on patients' characteristics (i.e., conscious sedation vs. anesthesia supported sedation). During the procedure, 8 biopsies will be obtained from the ilium, right and left colon.

- **Visit 6 – Exit Phenotyping**

- Visit 6 will occur within 7 days of Visit 3. Phenotyping will be performed as at the baseline phenotyping visit including the questionnaires performed in screening visit.

Primary Endpoint:

The primary endpoint is EEC function measured through satiety hormones' (GLP-1 & PYY AUC and absolute plasma value curves) comparison between intervention and placebo groups at day 90 in APS-OB phenotype participants.

Secondary Endpoint:

Evaluation of obesity phenotypes through gastric emptying T_{1/2} for solids, satiety sensation with a visual analogue scale (VAS), fullness (VAS), hunger (VAS), desire to eat (VAS), appetite overall score (VAS), ad-libitum buffet meal food intake (kcal), microbial changes, behavioral questionnaires, energy expenditure, and body weight in APS-OB phenotype participants intervened with IC-CBAS, compared to placebo.

Statistical Analysis:

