The primary analysis will compare AUC values between treatment and placebo groups after 90 days of IC-CBAS. Based on the previous study by Calderon et al.[1], we calculated a sample size of 36 subjects. They reported GLP-1 AUC significant difference between intervention and placebo group of 3223 mg/dl. We aim to detect a mean difference in AUC of 3223mg/dl and utilized their IQR to calculate a standard deviation of 3125mg/dl. To have 80% power to detect a difference of 3223mg/dl with a two-sample t-test would require 12 subjects per group. In order to allow for up to 30% dropout, we will enroll 36 subjects total. The effect on weight loss will be evaluated using analysis of covariance (ANCOVA) models, with relative weight loss as the dependent variable, adjusting for gastric emptying (T_{1/2}, min) and gender. Any power lost on degrees of freedom spent on covariate parameter estimation should be more than reclaimed by reduced error variation. For the rest of the endpoints we will compare the data on gastric emptying, satiation parameters, appetite scores, body composition, energy expenditure, GI hormones, bile acids and microbiota between intervention vs. placebo, using the same ANCOVA model. Transformations will be employed as needed for heavily skewed distributions. All treatment effect estimates will be reported with 95% confidence intervals.

POTENTIAL PITFALLS AND PRECAUTIONS TAKEN:

Potential pitfalls of minor significance in this study are:

- **Selection bias** - Participants willing to participate will likely be more motivated to lose weight than the general population. Randomization, double blind will avoid any selection bias;
- **Potential for type II error** - The sample sizes have been based on appropriate statistical power with allowance for drop out. Estimates of variation have been thoroughly characterized in the prior literature from our lab; and other internal and external studies for weight loss at 12 weeks.
- **Feasibility** - We have identified a cohort of people in our community who have obesity, abnormal satiety phenotype, and are willing to participate. We have the experience to successfully recruit 36 participants for the study.

Human Studies Aspects

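### The same 36 participants rest on two unreconciled calculations, and at two-sided 5% the GLP-1 AUC inputs give about 68% power at 12 per group, not 80%

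*Combined protocol and SAP*

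**What the plan says.** **Synopsis (Study design).** The number is attributed to an earlier weight trial ("Based on the results of our previous trial comparing weight loss in exenatide therapy vs placebo"), from which "we calculated a sample size of 18 participants per group (total of 36) with 80% power, 0.05 alpha to detect a 1 kg difference". No SD is given, and dropout is not mentioned.

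**Research Plan, Design.** "We plan to randomize 18 participants per group".

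**Primary and Secondary Endpoint.** "The primary endpoint is EEC function measured through satiety hormones", namely GLP-1 and PYY, at day 90. Weight is in the secondary list, which ends with "energy expenditure, and body weight in APS-OB phenotype participants intervened with IC-CBAS, compared to placebo".

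**Statistical Analysis.** The total of 36 is derived again, from a GLP-1 AUC difference of 3223 and an SD of 3125 back-calculated from an IQR: "To have 80% power to detect a difference of 3223mg/dl with a two-sample t-test would require 12 subjects per group". Then: "In order to allow for up to 30% dropout, we will enroll 36 subjects total". This section states neither alpha nor sidedness. It plans 95% confidence intervals for all treatment effects and analyses weight by ANCOVA "with relative weight loss as the dependent variable".

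**The concern.** Eighteen per group plays two roles. In the synopsis it is the calculated requirement for weight. In Statistical Analysis the requirement is 12, for GLP-1 AUC, and 18 is that number after the dropout allowance. One sample size can serve two endpoints, but then the plan should say so and say which endpoint sets it. As written, a reader of the synopsis takes the trial to be sized for weight at 80% power, although weight is secondary. The synopsis claim is also in kilograms, while the planned analysis is of relative weight loss.

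The second question is whether the primary-endpoint calculation delivers the power it states. The section on potential pitfalls answers the type II error risk by pointing to adequate power with dropout allowed for. If 12 completers per group do not give 80%, that reassurance fails at the very dropout level the plan says it covers.

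**Working it through.** **Inputs.** From Statistical Analysis: difference 3223, SD 3125, two-sample t-test, target power 80%, 12 per group, dropout up to 30%, 36 enrolled. Allocation is 1:1 (Randomization and treatment). Alpha 0.05 appears only in the synopsis. Sidedness is stated nowhere; the planned 95% intervals correspond to two-sided 5%.

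**Step 1: dropout allowance.** 12/(1 − 0.30) = 17.1, so 18 per group and 36 in total. This reproduces the plan.

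**Step 2: standardised difference.** d = 3223/3125 = 1.031. The units cancel.

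**Step 3: which test gives 12 per group?** Normal approximation: n per group = 2(z_alpha + z_power)²/d².
- Two-sided 5%: 2(1.960 + 0.842)²/1.031² = 14.8, so 15.
- One-sided 5%: 2(1.645 + 0.842)²/1.031² = 11.6, so 12.

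The stated 12 is therefore the one-sided answer under the normal approximation. That approximation gives 81% power at 12 one-sided and 71% two-sided.

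**Step 4: power of the t-test the plan names.** The noncentrality is d/√(1/n1 + 1/n2), with n1 + n2 − 2 degrees of freedom. At 12 per group it is 1.031 × √6 = 2.526 on 22 df, and the two-sided critical value is 2.074.

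| Completers per group | Two-sided 5% | One-sided 5% |
|---|---|---|
| 12 | 67.5% | 78.9% |
| 13 + 12 (30% loss: 36 × 0.7 = 25.2) | 69.4% | 80.4% |
| 13 | 71.3% | 81.8% |
| 15 | 77.8% | – |
| 16 | 80.6% | – |
| 18 | 85.2% | – |

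At two-sided 5% the requirement is 16 per group. With 18 enrolled, at most 2 per group (2/18 = 11%) can be lost before power falls below 80%.

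**Step 5: could covariate adjustment close the gap?** With two covariate degrees of freedom and d replaced by d/√(1 − R²), gastric emptying and gender would have to explain about 26% of the variance at 12 per group, or about 20% at 13, to restore 80% two-sided. The plan gives no figure.

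**Step 6: the weight claim.** It cannot be recomputed without an SD. Working backwards at two-sided 5%, 80% power for 1 kg implies an SD of about 1.04 kg if 18 per group are evaluable. It implies about 0.84 kg if 12 are, or about 0.87 kg if 13 are. The documents neither confirm nor refute any of these.

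**The case against.** The best defence is that the 12 is a correct one-sided calculation. The hypotheses are directional (hormone secretion is expected to rise), sidedness is never stated, and at 30% loss (13 + 12) one-sided power is 80.4%. This stands as far as it goes: 68% is conditional on a two-sided test, and a reader should not take it as the trial's established power. But no section declares a one-sided test, the 95% intervals point the other way, and even one-sided the named t-test gives 78.9% at 12 and needs 13. Either way the plan has to state what was used.

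It is also fair that 30% is an upper limit on dropout. If everyone completes, two-sided power is 85%. The same ANCOVA model is planned for the GI hormones and may recover some power. Both points soften the shortfall, but the sentence that 12 per group gives 80% was written for an unadjusted t-test and is not met at two-sided 5%.

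A reader might also infer that the weight claim is wrong, with power for 1 kg falling well below 80% once dropout occurs. The documents do not support that. The SD lies in a cited trial that is not available here, and the synopsis does not say whether its 18 is before or after dropout. The Design section randomizes 18 per group and the pitfalls section says the sizes allow for dropout; both lean towards 18 being the enrolled number, without settling it.

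**Conclusion.** The concern holds in two parts.

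- **Reconciliation.** Two current sections derive the same 36 from different endpoints with no cross-reference, and the synopsis attaches its only power statement to a secondary endpoint. This rests on the text alone.
- **Power.** At two-sided 5%, the reading best supported by alpha 0.05 and the 95% intervals, the GLP-1 inputs give about 68% at 12 per group and 69% at the full 30% loss, so the type II error there is about 31–32%, not 20%. Sixteen per group are needed. This assumes an unadjusted t-test and takes the IQR-derived SD at face value.

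The calculation covers GLP-1 only; PYY is also in the primary endpoint and has no sample-size figure. A reader might infer that the trial is too small or must enrol more. That does not follow: 18 per group gives 81–85% two-sided power if 16 to 18 complete, the study is described as proof of concept, and effects are reported with confidence intervals. What needs correcting is the stated power and its basis; randomization, conduct and analysis are unaffected.

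**What to change.** **Statistical Analysis.** State alpha and sidedness.
- If two-sided 5%, replace the statement that 12 per group gives 80% with power by completers for 18 enrolled per group: about 85% at 18, 81% at 16, 71% at 13 and 68% at 12 (difference 3223, SD 3125, unadjusted t-test).
- If one-sided 5% was used, declare it.

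**Synopsis.** Give the GLP-1 AUC calculation as the basis for 36. Either drop the 80% claim for 1 kg, or keep it labelled as secondary, with its SD, its scale (the planned analysis uses relative weight loss) and whether 18 is before or after dropout.

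**Cost.** Text only, with no change in enrolment. The downside is a less favourable stated power if the test is two-sided. Only if the sponsor wants two-sided 80% to survive 30% dropout would numbers rise: 16/0.7 = 22.9, so 23 per group and 46 in total, 10 more than planned.

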During the screening and consent visit, informed consent will be requested either in person or virtually through the e-consent process. We will request medical history, or perform a brief chart review if available, acquire most recent anthropometric parameters, (height, weight, and waist circumference) and we will request completion of questionnaires (Appendix A). The questionnaires will be administered via Redcap and will need to be filled after consenting to determine eligibility. Food and activity diaries will be given to the participants for filling during the following 7 days (baseline and treatment phase). An activity tracking device will also be given to be used throughout the complete study. A stool collection kit be provided to complete 48 hours prior to visit 1.

See appendix A: Questionnaires

Screening & phenotyping questionnaires:

1. GI Screening Bowel Disease Questionnaire
2. Hospital Anxiety and Depression Inventory
3. Bristol stool scale
4. Physical Activity Questionnaire
5. Eating Patterns Questionnaire
6. Body Self Relations Questionnaire

7. Audit C Questionnaire
8. Weight Management Questionnaire
9. Obesity Questionnaire
10. Exercise Regulations (BREQ-3) Questionnaire(survey)
11. Barriers to Being Active Questionnaire(survey)
12. Weight Efficacy Questionnaire(survey)
13. Three Factor Eating (TFEQ-R21) Questionnaire(survey)
- 14. Physical Exam and History Documentation**

Baseline phenotype:

Subjects will collect a random stool specimen 48 hours before visit 1. All the participants will be given an activity tracking device. This device needs to be picked up in the CRTU, alongside with the instructions on how to install it with its corresponding tracking app. They will be required to use this device during the time they are participating in the study. Physical activity data, caloric consumption and medication use will be entered by the participants via weekly diaries, as well as extracting physical activity data from each participant's tracking device account. A food diary will also be given to all participants to fill in the week prior during this week. All questionnaires will be sent and filled during this 7-day period in case they didn't complete them during the screening and consent.

- **Visit 1:** Baseline phenotype

Participants will attend Mayo Clinic Clinical Research Trial Unit (CRTU) at [REDACTED] Rochester MN after an 8-hour fasting period.

- They will undergo anthropometric measurements:

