Height, weight, blood pressure, heart and respiratory rates, waist and hip ratio, waist circumference, and temperature.
- Baseline and follow-up characteristics studies:
- Methods of metabolic studies:
 - o Body composition will be measured by DEXA (dual energy x-ray absorptiometry).
 - o Resting energy expenditure was assessed by indirect calorimetry with a ventilated hood (Parvo Medics, Sandy, UT).

- Gastric emptying (GE) of solids by scintigraphy [9] [8, 11] Images will be acquired at 0, 30, 60, 90, 120 and 240 minutes following the normal clinical gastric emptying testing protocol without a push meal.
- Satiation will be measured by *ad-libitum* meal to measure total caloric intake and macronutrient distribution in the chosen food. Satiation will be reported in calories consumed at fullness (satiation) [8] [11].
- Appetite sensations by visual analog score fasting and every 30 minutes after the standard meal for GE and the Satiation test up to 2 hours [8, 11].
- Blood samples: The fasting blood samples will be collected during the gastric emptying meal and stored at -70° C freezer. We will analyze plasma glucose, insulin, C-peptide, GLP-1, PYY₃₋₃₆, OXM, FGF-19, 7- α -C4, Adiponectin, Leptin, CCK, Pancreatic Polypeptide (PP), serum bile acids, short chain fatty acids, amino acids[2, 8]. Samples collection, handling, and storage: Samples will be collected after an overnight fast (of at least 8 hours) in the morning. Plasma will be preserved following standard guidelines and protein degradation inhibitors, kallikrein and DPP-IV inhibitors will be added to preserve the samples. Samples will be stored at -80°C in the PI's laboratory. Plasma hormones and proteomics by radioimmunoassay and/or mass spectrometry measured fasting, postprandial, and every 30 minutes for 6 hours. The primary endpoint being the peak postprandial level (test should be done simultaneously to GE).
- Blood DNA for genome wide association studies (GWAS). These samples will be stored for future research.
- Stool samples: One random stool will be collected at baseline and after treatment for fecal bile acids, short chains fatty acids and microbiome.
- Participants with childbearing potential will undergo a pregnancy test.
- Self-administered questionnaires assessing affect, physical activity levels, attitudes, body image, diet, and eating behavior; details of each questionnaire are provided below.

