All participants will meet with a study physician as standard of care in clinical practice. All participants will guided to 1) Diet: Reduce dietary intake below that required for energy balance by consuming 1200 calories per day for women and 1400 calories per day for men; 2) Physical Activity: reach the goal of 10,000 steps or more per day; 3) Exercise: reach the goal of 150 minutes or more of cardiovascular exercise/week; 4) Limit consumption of liquid calories (i.e. sodas, juices, alcohol, etc.).

- **Visit 2: Colonoscopy #1 and Randomization**

- Visit 2 will only be completed in the first 6 patients of each group who are willing to consent to both colonoscopy visits.
- Visit 2 will occur 3- 5 days of Visit 1. Participants will receive a bowel prep (Movi-prep) during Visit 1 and follow standard colonoscopy preparation guides. The next day, after an overnight fasting, a colonoscopy with terminal ileum intubation will be performed. The colonoscopy will be done in the GI clinical or research unit and will be supported by sedation based on patients' characteristics (i.e., conscious sedation vs. anesthesia supported sedation). During the procedure, 8 biopsies will be obtained from the ilium, right and left colon.
- Randomization and treatment:
Randomization will be performed by the research pharmacy upon notification by the study coordinator. Treatments will be allocated at a 1:1 ratio stratified within low, medium, or high gastric emptying (T1/2) rates, based on sex-specific thresholds. The stratification group will be determined by the study coordinator and communicated to the pharmacist. A computer application will provide the randomized assignment based on a randomization schedule created by the study statistician. Only the study statistician will have access to the complete schedule. Other study personnel and the subject will be blinded to assigned treatment.

Patients will receive study medication (active or placebo), and they will be given verbal instructions on how they should take their medications. Subjects will take medication or placebo orally twice daily on an empty stomach, 30 minutes prior to breakfast and evening dinner for 90 (+/- 5) days. Patients will be instructed to start the medication after visit 2 (colonoscopy).

- **Visit 3: Study Team visit**

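### The stool collection method is stated two ways, and nothing stops the exit stool from following the exit bowel prep in up to 12 of 36 participants

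*Combined protocol and SAP*

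**What the plan says.** **Method.** The Design section of the research plan lists stool among the phenotype-visit procedures: "Stool samples will be collected for 24 hours for microbiome, bile acids and short chain fatty acids". The Visit 1 stool bullet covers the same three analyte groups: "One random stool will be collected at baseline and after treatment for fecal bile acids, short chains fatty acids and microbiome". The Baseline phenotype section agrees with that bullet: "Subjects will collect a random stool specimen 48 hours before visit 1".

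**Baseline order.** The stool precedes Visit 1. For the colonoscopy subset, the Visit 2 section then says "Participants will receive a bowel prep (Movi-prep) during Visit 1 and follow standard colonoscopy preparation guides", and "Visit 2 will occur 3- 5 days of Visit 1".

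**Exit order.** The Visit 5 section says "Participants will receive a bowel prep (Movi-prep) during visit 5 and follow standard colonoscopy preparation guides", with the colonoscopy on the following day. Visit 6 is exit phenotyping, done in the same way as baseline phenotyping. The Design section lists the two visits in the same order. The exit stool is timed only as after treatment. Its position relative to the exit prep is not stated.

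**Use of the data.** Microbial change is a listed secondary endpoint. The Statistical Analysis section compares bile acids and microbiota between arms by an ANCOVA adjusted for gastric emptying and gender.

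**The concern.** There are two separate problems.

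First, a timed 24-hour collection and a single random stool measure different things. For bile acids and short chain fatty acids, the first supports a daily output and the second only a concentration. Staff working from different sections could record different variables under one name, and no sentence says which section governs.

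Second, a bowel prep empties the colon. If the exit stool of colonoscopy participants is taken after it, their exit values reflect the prep as well as the treatment. The baseline stool carries no such effect, and participants without colonoscopy have none at either time. The planned ANCOVA has no term for colonoscopy, so it would not absorb the difference.

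At stake are the microbiome endpoint and the fecal bile-acid comparison. The protocol's summary and background report that fecal bile acids were associated with weight loss in the earlier trial, so a clean measurement is worth having.

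**Working it through.** **1. Method, side by side**

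| Section | Collection | Applies to |
|---|---|---|
| Design | 24 hours | phenotype visits, no distinction between baseline and exit |
| Baseline phenotype | random specimen, 48 hours before Visit 1 | baseline |
| Visit 1, stool samples | one random stool | baseline and after treatment |

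The conflict is between sections. Each section read alone applies one method throughout.

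**2. Size of the subset**

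The summary's Study design section gives 6 participants per group with colonoscopy, 12 patients and 24 procedures in total. Check: 6 × 2 = 12 patients; 12 × 2 = 24 procedures. Both agree. Enrollment is 36, so the share is 12/36 = 33.3%.

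The Statistical Analysis section allows up to 30% dropout: 36 × 0.7 = 25.2 completers. With proportional dropout the subset is 12 × 0.7 = 8.4, and 8.4/25.2 is still 33.3%.

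**3. Baseline timing**

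Stool is collected 48 hours before Visit 1, and the prep is handed out at Visit 1. The baseline stool therefore precedes the prep by at least 48 hours.

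**4. Exit timing**

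Three assumptions are needed, because the documents do not settle this:
- Visit 6 falls *d* days after the exit colonoscopy, with *d* from 0 to 7. The protocol gives Visit 6 a 7-day window, but ties it to Visit 3.
- The prep is taken the day before the colonoscopy, at day −1.
- The 48-hour baseline rule carries over, so stool is collected at day *d* − 2.

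Stool day minus prep day = (*d* − 2) − (−1) = *d* − 1.

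| *d* | Exit stool relative to prep |
|---|---|
| 0 | 1 day before |
| 1 | same day |
| 2 to 7 | 1 to 6 days after |

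On these assumptions the stool follows the prep for 6 of the 8 offsets. This counts possibilities; it is not a probability.

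**5. Why the exit order is not settled**

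- The Visit 6 section ties that visit to Visit 3, about 30 days after Visit 2. The Methods section puts exit phenotyping at Day 90 (± 5).
- The Study design section places the exit colonoscopy after the last dose. The Methods section has study drug or placebo given at exit phenotyping, before the test meal. Both cannot hold if Visit 6 follows Visit 5.

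**6. Possible dilution**

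Suppose a fraction *f* of the treatment difference in a stool measure is lost in participants sampled after prep, and one third of each arm is affected. The between-arm difference is then multiplied by 1 − *f*/3. The documents give no value for *f*. Over the whole range: *f* = 0 gives 1.00, *f* = 0.5 gives 0.83, and *f* = 1 gives 0.67.

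**The case against.** The strongest reply is that little has been shown to go wrong. The visit-level text is consistent on a random stool, and the Design sentence may be a leftover. The exit stool is timed only as after treatment; the 48-hour rule is written for Visit 1 and reaches Visit 6 only by inference. The prep is the same in both arms, with 6 planned in each, and the planned comparison is between arms. The stool measures are not primary and carry no sample-size claim.

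Most of this stands, and it rules out several stronger readings.

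- *A reader might infer that the method conflict means baseline and exit are measured differently.* They are not, on either text: the Visit 1 bullet sets one method for both time points, and the Design section makes no distinction.
- *A reader might infer that the exit stool does follow the prep in 12 of 36.* The documents fix no such time, so 12 is a planned maximum.
- *A reader might infer that nearly half of the analyzed participants are affected*, from 12/25.2 = 48%. That requires all 10.8 expected dropouts to come from the 24 participants without colonoscopy (10.8/24 = 45%) and none from the subset.
- *A reader might infer a sample-size penalty for using a concentration in place of daily output.* That needs a correlation between the two, which the documents do not give. It would also treat daily output as the target, which the plan does not say.

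The reply does not remove the contradiction in method, or the lack of any rule keeping the exit stool clear of the prep. Balance between arms protects against a directional error, but not against noise or dilution.

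**Conclusion.** The point holds in two limited parts.

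The stool method is contradictory for the same analytes and must be reconciled. This rests on the text alone.

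The exit stool may follow the exit bowel prep in up to 12 of 36 participants (33%), whereas the baseline stool precedes any prep. This rests on the listed order of Visits 5 and 6 and on repeating the baseline procedure at exit. The likely effect is added noise or a smaller apparent difference in the microbiome and fecal bile-acid comparisons. Directional bias between arms is not expected while the subset stays at its planned 6 per arm. The documents give no basis for a firmer size than the illustrative range shown.

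This is a low-severity point about non-primary measures, worth acting on because the repair costs almost nothing.

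**What to change.** 1. **State one stool method and use it at both time points.** Random stool is the smaller edit, because the Baseline phenotype and Visit 1 sections already specify it and only the Design sentence changes. The cost is that daily bile-acid output cannot be reported, only concentrations. A 24-hour collection used throughout would also resolve the conflict, with more text to change and more work for participants.
2. **Time the exit stool.** In colonoscopy participants, collect it at the end of the treatment period and before the exit bowel prep, with the same method and pre-visit window as at baseline. The cost is a line of protocol text and handing out the exit stool kit earlier. Record the dates of stool and prep so that any departure can be seen.
3. **Reconcile the exit schedule.** The Visit 6 window tied to Visit 3, the Day 90 exit visit in Methods, and the order of last dose, exit colonoscopy and exit phenotyping across the Study design, Methods and visit sections must be made to agree. Which order is right is for the investigators to decide; the stool timing should then be written against it.
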